4. OBJECTIVES AND ENDPOINTS

The objectives and endpoints are described in [Table 3](#).

Table 3: Objectives and Endpoints

Objectives	Endpoints
Primary	

 To evaluate the proportion of patients with obesity with genetic variants in a specific gene in the MC4R pathway who achieve a clinically meaningful reduction in body weight in response to setmelanotide at the end of open-label treatment 	
 The proportion of patients by genotype who demonstrate a significant clinically meaningful response (defined below) to setmelanotide at the end of Stage 1: 
 For all patients: achieving a $\geq 5\%$ reduction in BMI from Baseline
Secondary	

 To evaluate change in weight parameters and hunger in response to setmelanotide in patients with genetic variants in a specific gene in the MC4R pathway at the end of open-label treatment 	
 Mean change and percent change in BMI from Baseline to end of Stage 1 in all patients and patients ≥ 18 years old, per gene Mean change and percent change in body weight from Baseline to end of Stage 1 in patients ≥ 18 years old, per gene Mean change in BMI Z-score from Baseline to end of Stage 1 in patients < 18 years old, per gene Mean percent change in the weekly average of the daily maximal hunger score from Baseline to end of Stage 1 in patients ≥ 12 years old, per gene The proportion of patients ≥ 12 years old, per gene, who achieve a ≥ 2-point reduction (improvement) from Baseline to end of Stage 1 in the weekly average of the daily maximal hunger score
[REDACTED]	[REDACTED]
[REDACTED]	[REDACTED]

Table 3: Objectives and Endpoints

Objectives	Endpoints
[REDACTED]	[REDACTED]
[REDACTED]	[REDACTED]
[REDACTED]	[REDACTED]

Table 3: Objectives and Endpoints

Objectives	Endpoints
	
[REDACTED]
 
[REDACTED]
 
[REDACTED]
 
[REDACTED]
 
[REDACTED]
 
[REDACTED]
 
[REDACTED]
 
[REDACTED]
 
[REDACTED]
 
[REDACTED]

Safety	

 To evaluate the safety and tolerability of setmelanotide in patients with genetic variants in the MC4R pathway 	
 Safety and tolerability assessed by the frequency and severity of AEs, changes in vital signs, and changes in laboratory evaluations at the end of Stage 1 and Stage 2

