6.3. Treatment Discontinuation and Withdrawal from the Trial

Given this rare patient population, every effort should be made to encourage and keep patients enrolled in the trial until completion, unless there are any safety concerns necessitating withdrawal of the patient. The Sponsor will provide assistance for patient and caregiver travel and will provide other necessary logistical support to ease the burden on the patient in order to facilitate compliance and completion of trial participation.

Discontinuation of trial treatment or skipped visits/injections may be allowed without withdrawal from the trial.

Some patients' reason for discontinuation may be related to injection site reactions and burdensome laboratory/visits. Patients can be offered the option to discontinue trial medication but remain in the trial. These patients who stop therapy will be counted as a non-responder, irrespective of treatment assignment. However, they will be followed and have weight assessments at each visit, particularly at the final visit to determine weight trajectory for all patients. Patients who withdraw before completing Visit 14 are to attend an Early Termination visit within 14 days (± 7 days) after the last dose of trial medication for final trial assessments. If possible, patients will be asked to determine weight assessment at the expected time of their EOT visit.

If the patient withdraws consent for disclosure of future information, the Sponsor may retain and continue to use any data collected before such a withdrawal of consent.

If a patient withdraws from the trial, he/she may request destruction of any samples taken and not tested, and the Investigator must document this in the site trial records.

Patients will be informed that they have the right to withdraw from the trial at any time for any reason, without prejudice to their medical care. The Investigator also has the right to withdraw patients from the trial for reasons such as:

- AEs, which in opinion of Investigator justifies treatment or trial withdrawal. For specific predefined events, additional monitoring and guidance for the Investigator is provided in [Appendix 5](#).
- Non-adherence to trial medication regimen or protocol requirements.
- Non-compliance with instructions or failure to return for follow-up.

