In general, unless otherwise specified, events or measurements happen before the randomization date are in Stage 1 and happen on or after the randomization date are in Stage 2. For patients who are not randomized, all events or measurements are in Stage 1. All events happening after visit 14 will not be considered as in Stage 2 for patients who enrolled into bridging visit unless otherwise specified.

D. Definition of Baseline

Baseline Definition

Baseline will be defined as the last non-missing measurement taken prior to the start of stage 1 open-label treatment administration. In the case where the last non-missing measurement and the reference start date coincide and time of measurement is not available, that measurement will be considered Baseline unless the assessment was scheduled to be post-study drug administration in the SOA. Change from baseline is defined as the post-baseline value minus the baseline value, unless specified otherwise. Percent change from baseline = $(\text{Change from Baseline}/\text{Baseline}) \times 100$.

Study Day

Study Day will be calculated from the reference start date within stage and will be used to show start/stop day of assessments and events. Reference start date is defined as the day of first dose (Day 1) in stage1.

Study Day will be computed as follows:

(Confidential)

- Study Day = (date of event - date of first dose in stage 1) + 1 if the date of the event is on or after the date of first dose.
- Study Day = (date of event - date of first dose in stage 1) if the date of the event is prior to the date of first dose.

E. Missing Data

Unless stated otherwise, missing data will not be replaced with imputed values. When relevant, sections below will address how missing data will be handled for the particular analyses.

Analysis Window

All measurements recorded at unscheduled or early termination visits will be mapped according to the windowed visits by actual study day. These records then will be used for analysis if the scheduled ones are missing. If more than one visit occurs within a single visit window, then the analysis will take the one closest to and before the target day. All scheduled assessments will be analyzed according to the protocol defined visits, regardless of the study day

Stage	Study Visit	Study Week	Study Day	Study Day Window
1	Enrollment Visit	1	1	1
1	Virtual Visit 2	2	14	Post-dose - 21
1	Virtual Visit 3	4	28	22 - 35
1	Virtual Visit 4	6	42	36 - 49
1	Visit 5	8	56	50 - 70

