1	Virtual Visit 6	12	84	71 - 98
1/2	In-Person Clinic Visit 7	16/End of Stage 1	112	Patients enrolling in Stage 2: 99 to first dose of Stage 2 Patients not enrolling in Stage 2: 99 - 117
2	Virtual Visit 8	18	126	Post-dose - 133
2	Virtual Visit 9	20	140	134 - 154
2	In-Person Clinic Visit 10	24	168	155 - 182
2	Virtual Visit 11	28	196	183 - 210
2	In-Person Clinic Visit 12	32	224	211 - 238
2	Virtual Visit 13	36	252	239 - 266
2	End of Treatment Visit 14	40	280	266 - 283

Primary Efficacy Endpoint Missing Data Imputation

For patients who do not have BMI value at the end of Stage 1 (Week 16), the unscheduled or early termination weight measurement mapped into Week 16 per visit window will be used for the primary analysis. If weights are measured in triplicate within a same date, the average of the triplicates will be calculated before the BMI calculation. The latest height value will be used together to derive the missing Week 16 BMI.

For patients who still do not have BMI value after above imputation at Week 16, they are treated as non-responder for the primary.

Missing or Partial Adverse Event and Medication Start or Stop Date:

For partial start dates:

- If the year is unknown, no imputation will occur.
- If the year is known and the month and day is unknown, then:
 - If the year matches the year of the first dose date, then impute the month and the day the same as first dose date.
 - If the year is not the same year of the first dose, then month and day will be imputed as 01 January.
- If the month and year is known and the day is unknown, then:
 - If the month and year match the month and year of the first dose date, then impute the day the same as first dose date.
 - If year and month is not the same as the first dose date, then the day will be imputed as "01".

For partial end-dates:

- If the year is missing, no imputation will be performed, and the AE/CM will be assumed as ongoing.
- If the year is present and both month and day are missing and the year is not the same as the last study date, then the month and day will be imputed as the last day of the year, 31 December.
- If the year is present and both month and day are missing and the year is the same as the last study date, then the month and day will be imputed as the last study date.
- If the year and month are present and only the day is missing, and the year and month is not the same as the last study day then the day will be imputed as the last day of the month.

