The summary statistics displayed will be a function of the type of data associated with the summarized assessment. Unless stated otherwise in relevant sections to follow, continuous data will be summarized with the number of nonmissing values, mean, standard deviation, minimum, first quartile (Q1), median, and maximum, third quartile (Q3). Categorical data will

be summarized with the number of nonmissing values and the numbers of values equal to each of the possible values. Percentages of patients with each of the possible values will be calculated from the number of patients in the corresponding analysis population, unless stated otherwise. Some continuous variables may also be grouped into categorical levels and evaluated in frequency tables.

O. Blinded Review of Data

After all study data have been collected but prior to examining any study outcome data by treatment group, the data will be reviewed by the study statistician to determine whether any clarifications or changes to the analysis plan are needed. Any revisions made to the analysis plan as a result of the blinded review of the data will be documented.

P. Software Version

All analyses will be conducted using SAS Enterprise Guide 7.1 (64-bit) or SAS version 9.4 (64-bit).

Q. Gene Cohort Analysis

Gene cohort in this SAP is defined as group of patients with specified primary gene(s). In details, please see below for the grouping:

Gene Cohort	Genotype
SEMA3 Pathway	NRP1, NRP2, PLXNA1, PLXNA2, PLXNA3, PLXNA4, SEMA3A, SEMA3B, SEMA3C, SEMA3D, SEMA3E, SEMA3F, SEMA3G
PHIP	PHIP
SIM1	SIM1
MAGEL2	MAGEL2
Other	TRPC5, MRAP2, HTR2C, KSR2, TBX3, LEP, ISL1, DNMT3A, MECP2, MC3R, CPE, RPGRIP1L, CREBBP, TUB

After a patient enrolls in the trial, the pre-identified primary gene is reconfirmed or may be reclassified with the [REDACTED] and manual blind review during the trial. A supplemental analysis with the re-confirmative classification of genes will be conducted.

VI. Patient Accountability

All patients in safety analysis set will be used for below analyses unless otherwise specified. The table and listing display for all analyses below will follow section V.N unless otherwise specified.

A. Patient Demographic and Baseline Characteristics

Patient demographic and baseline characteristics will include the patient's age [6 to <12, 12 to <18, and 18 to ≤65 years of age], sex [Child-bearing potential if female], ethnicity, race, weight

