Medical history will be coded using Medical Dictionary for Regulatory Activities (MedDRA) version 24.1 Medical history will be tabulated by system organ class and preferred term. A listing of medical history will be provided.

VII. Efficacy Analyses

The analysis of the efficacy endpoints in Stage 1 will be performed based on the safety analysis set, and the analyses of the efficacy endpoints in Stage 2 will be performed based on the full analysis set (FAS). End of Stage 1 in below section will refer to the measurement collected at Week 16 and end of Stage 2 will refer to Week 40, unless otherwise specified. The tabulation and listing formats for all analyses below will follow section V.N unless otherwise specified.

A. Efficacy Assessments

A.1 Weight

Weight should be measured after patients have attempted to empty their bladders and after fasting for at least 8 hours. Patients are to wear light clothing or underwear and no shoes, with empty pockets and will be weighed at approximately the same time of day. All measurements will be recorded to the nearest 10th of a kg if reported with a digital scale, or half kg with a mechanical scale. Weight measurements will be collected in triplicate. Only in-person visits measurements will be summarized in tables.

[REDACTED]

[REDACTED]

[REDACTED]

[REDACTED]

[REDACTED]

[REDACTED] (Confidential) [REDACTED] [REDACTED]

[REDACTED]
[REDACTED]
[REDACTED]

[REDACTED]
[REDACTED]
[REDACTED]

[REDACTED]
[REDACTED]

[REDACTED]
[REDACTED]

[REDACTED]
[REDACTED]

[REDACTED]
[REDACTED]
[REDACTED]
[REDACTED]

[REDACTED]
[REDACTED]

[REDACTED]
[REDACTED]
[REDACTED]
[REDACTED]

[REDACTED]
[REDACTED]
[REDACTED]
[REDACTED]

[REDACTED]
[REDACTED]
[REDACTED]
[REDACTED]

[REDACTED]
[REDACTED]

[REDACTED]

[REDACTED]

[REDACTED]

VIII. Questionnaires

All patients in safety analysis set will be used for below analyses in Stage 1 and FAS in Stage 2 unless otherwise specified. The tabulation and listing formats for all analyses below will follow section V.N unless otherwise specified.

[REDACTED]

[REDACTED]

[REDACTED]

[REDACTED]

[REDACTED]

[REDACTED]

[REDACTED]

[REDACTED]

[REDACTED]

[REDACTED]

[REDACTED]

[REDACTED]

[REDACTED]

[REDACTED]

[REDACTED]

[REDACTED]

[REDACTED]

[REDACTED]

[REDACTED]

[REDACTED]

[REDACTED]

[REDACTED]

[REDACTED]

[REDACTED]

[REDACTED]

[REDACTED]

[REDACTED]

[REDACTED] (Confidential) [REDACTED] [REDACTED]

[REDACTED]
[REDACTED]
[REDACTED]
[REDACTED]
[REDACTED]

[REDACTED]

[REDACTED]

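### On the readable SAP rules, treated patients with no in-person value at Week 16 count as non-responders in the primary but are absent from the Stage 1 mean changes

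*SAP*

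**What the plan says.** The rules that bear on this point sit in several places.

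- **Endpoint and analysis set.** Protocol Section 4 (Table 3) lists as a secondary endpoint the "Mean change and percent change in BMI from Baseline to end of Stage 1 in all patients", reported per gene. Weight change is defined for adults and BMI Z-score change for patients under 18. SAP VII bases Stage 1 efficacy on the safety analysis set, which is everyone dosed at least once.
- **Time point.** SAP VII states: "End of Stage 1 in below section will refer to the measurement collected at Week 16".
- **Default for missing data.** SAP V.E: "Unless stated otherwise, missing data will not be replaced with imputed values". The next sentence adds: "When relevant, sections below will address how missing data will be handled for the particular analyses".
- **Summary rule.** SAP V.N: "continuous data will be summarized with the number of nonmissing values, mean, standard deviation", followed by the usual order statistics.
- **Source of tabulated weights.** SAP VII.A.1 (Weight): "Only in-person visits measurements will be summarized in tables".
- **Primary endpoint only.** SAP V.E has a separate rule for the primary. An unscheduled or early-termination weight mapped to Week 16 is used, with the latest height. If BMI is still missing, "they are treated as non-responder for the primary".
- **Window.** In SAP V.E, Week 16 runs from Day 99 to Day 117 for patients not entering Stage 2. Unscheduled and early-termination values inside a window replace a missing scheduled value.
- **Withdrawn patients.** Protocol 6.3 sets the Early Termination visit at 14 days (plus or minus 7) after the last dose and adds: "If possible, patients will be asked to determine weight assessment at the expected time of their EOT visit".

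**The concern.** Read together, these rules give two answers to the question of who is counted at the end of Stage 1. The responder rate has every dosed patient in its denominator and scores the unmeasured ones as failures. The mean changes describe only those measured, although the analysis set is everyone dosed and the BMI endpoint is worded for all patients. Both results would appear in the same table set, per gene cohort, without a stated link.

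The cohorts are small. Protocol 5.1.4 aims for up to 10 patients per gene, and SAP V.N tabulates each SEMA3 gene separately. One or two absent patients can shift such a mean visibly. If leaving is related to poor response or poor tolerability, the shift favours the drug. Protocol 6.3 mentions injection-site reactions as one possible reason for stopping treatment.

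Some usable data may also go unused. A weight taken at home inside the Week 16 window would not be tabulated under VII.A.1. The primary's mapping rule shows no in-person limit, so an unscheduled home weight in the window could feed the primary but not the mean.

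**Working it through.** The plan states no dropout rate, effect size or statistical basis for sample size, so there is no planned figure to reproduce. The check has two parts: who is left out, and how much that could matter.

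**1. Who is left out**

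Inputs: Week 16 window Day 99 to 117 (SAP V.E, patients not entering Stage 2); Early Termination visit at the latest 14 + 7 = 21 days after the last dose (Protocol 6.3).

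A visit at a given lag falls in the window if the last dose was between Day 99 minus the lag and Day 117 minus the lag:

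| Lag from last dose to visit | Last-dose days that map to Week 16 |
|---|---|
| 0 days | 99 to 117 |
| 7 days | 92 to 110 |
| 14 days | 85 to 103 |
| 21 days | 78 to 96 |

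The earliest possible last dose is Day 99 - 21 = 78. A patient who leaves the trial with a last dose before Day 78 cannot supply a Week 16 value from an on-time Early Termination visit. A leaver with a later last dose may or may not, depending on the lag. The Early Termination visit is in person (Protocol Table 1), so a value in the window also satisfies VII.A.1.

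**2. How much it could matter (all values assumed)**

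Let d be the share of treated patients without a usable Week 16 value, m the mean change among those with one, and r the leavers' true Week 16 change as a fraction of m.

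- Tabulated mean: m
- Mean over all treated: (1 - d)m + d·r·m = m[1 - d(1 - r)]
- Relative overstatement: 1/[1 - d(1 - r)] - 1

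| d | r = 0 | r = 0.5 | r = 1 |
|---|---|---|---|
| 10% | 1/0.90 - 1 = 11% | 1/0.95 - 1 = 5% | 0 |
| 20% | 1/0.80 - 1 = 25% | 1/0.90 - 1 = 11% | 0 |
| 30% | 1/0.70 - 1 = 43% | 1/0.85 - 1 = 18% | 0 |

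Example with 10 patients, 8 stayers averaging -6.0% and 2 leavers:

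- Tabulated: -6.0%, from 8 patients.
- All treated, leavers at 0: (8 × -6.0 + 2 × 0)/10 = -4.8%.
- All treated, leavers at -2%: (8 × -6.0 + 2 × -2)/10 = -5.2%.

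Over stayers' means of -4% to -8%, leavers at 0 or -2%, and 10% to 40% missing, the gap runs from 0.2 points (-4.0 against -3.8) to 3.2 points (-8.0 against -4.8).

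The mismatch with the primary can be shown the same way. Take 10 patients, 3 without a Week 16 value and 5 responders. The primary is 5/10 = 50.0% (exact 95% CI 18.7 to 81.3). The mean beside it comes from 7 patients. On that same basis the responder rate would be 5/7 = 71.4% (29.0 to 96.3).

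**The case against.** The strongest reply is that the text which would settle the matter is not readable. SAP V.E says later sections may deal with missing data, and everything in SAP VII after the Weight paragraph is redacted. A reader might infer that the plan has no rule for the secondary means; the documents do not support that. This stands, and the request is therefore to confirm a rule or add one.

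Other tempting readings also go too far:

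- **All early discontinuers are lost.** They are not. The window rule in V.E admits early-termination values between Day 99 and Day 117 for any analysis. Patients who stop drug but attend Week 16 are measured and included.
- **The in-person limit covers BMI and BMI Z-score.** It is visible only under Weight (similar wording appears under Vital Signs). Carrying it over is an inference, because BMI is derived from weight.
- **The means breach the treatment-policy estimand.** The SAP's estimand table is written for the responder endpoint only. The argument rests on the analysis set and the endpoint wording.
- **The weight requested in Protocol 6.3 is a Week 16 weight.** End of treatment is Day 112 or Day 280, and the expected date for someone leaving in Stage 1 is not stated.
- **The means are biased in favour of the drug.** No dropout rate or leaver outcome is given, so neither direction nor size is established.

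It is also fair that V.N already shows the number of non-missing values, that disposition is tabulated and recorded data are listed, and that observed-case summaries are conventional in a descriptive Phase 2 trial without testing. Many reported means pool genes (13 in the SEMA3 cohort, 14 in Other), so the 10-patient example does not describe every table. These points lower the weight of the concern. They do not reconcile the two treatments of the same patients.

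**Conclusion.** On the readable rules the inconsistency holds. A treated patient with no in-person value at or mapped to Week 16 is a non-responder in the primary and absent from the mean change in weight, and by inference in BMI and BMI Z-score. The clearest case is a patient who leaves the trial with a last dose before Day 78.

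The size is conditional. It is zero if leavers match stayers. It is 11% to 43% of the true mean at 10% to 30% missing if leavers are back at baseline, and 5% to 18% if they keep half the effect. All of these inputs are assumed. The conclusion also depends on the redacted sections holding no exception. This is an inexpensive improvement to the plan. It does not show that the Stage 1 results would be wrong.

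**What to change.** Unless the redacted text already does this, two changes should be made before the Stage 1 analyses that SAP V.J schedules for the end of Stage 1:

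1. In SAP VII.A.1, allow a remotely collected weight inside the Week 16 window when no in-person weight exists, and flag it as remote. Include a withdrawn patient's weight taken around Day 112. Derive BMI from the latest height, as V.E already does for the primary.
2. Beside each Stage 1 mean change in BMI, weight and BMI Z-score, add a sensitivity mean over the treated patients to whom the endpoint applies, with a missing Week 16 value set to zero change. This mirrors the primary's non-responder rule.

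A repeated-measures model using all Stage 1 visits is optional. It would need a height rule for patients under 21, because Protocol Table 1 schedules no height at virtual visits.

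The cost is SAP wording and extra table rows, with no new visits, data or patients. The downsides are some between-scale error from home weights and a sensitivity estimate that may be smaller than the tabulated mean.

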17 Safety laboratory tests will include: Complete blood count (CBC) with platelet count and standard indices, chemistry panel (includes sodium, potassium, chloride, CO₂, albumin, total protein, glucose, blood urea nitrogen [BUN], creatinine (including eGFR), uric acid, aspartate aminotransferase [AST], alanine aminotransferase [ALT], gamma-glutamyl transferase [GGT], creatine phosphokinase [CPK], alkaline phosphatase, total bilirubin, direct bilirubin, lactate dehydrogenase [LDH], calcium, phosphorus), and urinalysis with microscopic analysis if positive findings on dipsticks warrant further examination. Safety

laboratories will also include a coagulation profile (prothrombin time [PT] or international normalized ratio [INR], and partial thromboplastin time [PTT] also referred to as activated PTT [aPTT]).

- ¹⁸ A blood sample for PK will be drawn at the time points indicated before dosing, with dosing performed at the clinic. PK samples will be drawn with patients/caregivers being reminded there should be NO trial medication administration at home on the day of clinic visits; the drug will be administered in the clinic by the patient AFTER the PK sample is obtained. For the PK sample, the actual collection (clock) time will be recorded.
- ¹⁹ Any patient with a positive ADA will be followed every 3 months after the ADA sample analysis until resolution of the ADA.
- ²⁰ A biomarker blood sample will be collected for metabolic, inflammation, metabolomic and/or proteomic biomarker analysis. This sample may not be analyzed. All samples are sent to a central laboratory. Additional details are described in the laboratory manual.
- ²¹ A daily question querying whether the patient completed their daily injection will be asked via electronic diary. Paper versions can be used, if needed.
- ²² Dispensing will be made by site staff, using the dispensation function in the Interactive Response Technology (IRT) system, as outlined in the SoA. Dispensing may also be made directly to the patient if required and allowed by local regulations. At the Early Termination visit, only drug return will apply.
- ²³ If at any time during the trial an individual patient's PHQ9 score is ≥ 10 , the patient should be referred to a Mental Health Professional.
- ²⁴ The CDI-2 will be administered to patients <12 years of age (self-report short form) and to caregivers of patients <12 years of age (parent version).

Table 2: Schedule of Assessments – Stage 2

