5.2. Patient and Trial Completion

A patient is considered to have completed the trial if he/she has received the last planned dose of trial medication on Study Day 280 and completed the EOS telephone visit on Day 308.

Patients who discontinue before completing the Study Day 280 EOT visit are to attend an Early Termination visit within 14 days (± 7 days) after the last dose of trial medication for final trial assessments.

The end of the trial is defined as the date of the last visit of the last patient under the auspices of the current trial.

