Items on the CDI-2 Parent form correspond to items on the self-report version and are suitably rephrased. Item selection for the parent forms was guided to maximize validity, and thus focused on observable manifestations of depression. The CDI-2 parent form consists of 17 items and the 4 choices provided for each item correspond to 4 levels of symptomatology: 0 (not at all), 1 (some of the time), 2 (often), or 3 (most of the time). The CDI-2 parent version will be administered to caregivers of patients < 12 years of age according to the SoA. Any patient with a CDI-2 score > 20 during the trial will be referred to an MHP.

X. Supplemental Analysis

A supplemental analysis deriving from re-confirmatory genetic diagnosis is conducted for Primary endpoint, and Secondary endpoints of efficacy for patients in Supplemental Analysis Set.

Patients who become ineligible for the trial after the re-confirmatory genetic diagnosis will be excluded from the supplemental analysis.

XI. Pharmacokinetic Analysis

The trough concentration values will be reported descriptively as mean, standard deviation (SD), maximum (Max), minimum (Min), median, and percent coefficient of variation (% CV) based on dose and visit.

The PK concentration and ADA will be listed.

██████████ (Confidential) ██████████ ██████████

XIII. Appendix 1: BMI-for-age charts, 2 to 20 years, LMS parameters and selected smoothed BMI (kilograms/meters squared) percentiles, by sex and age

Sex	Age (months)	L	M	S	P95	Age at Screen
M	24	-2.01118	16.57503	0.080592	19.33801	2
M	36.5	-1.41999	16.0003	0.072634	18.23842	3
M	48.5	-1.71487	15.62817	0.071889	17.83614	4
M	60.5	-2.61517	15.41914	0.075992	17.93893	5
M	72.5	-3.21171	15.38353	0.083048	18.41421	6
M	84.5	-3.32319	15.51287	0.092131	19.15236	7
M	96.5	-3.18306	15.78231	0.102091	20.06793	8
M	108.5	-2.97115	16.16712	0.111721	21.08893	9
M	120.5	-2.76565	16.64614	0.120112	22.15409	10
M	132.5	-2.59056	17.20089	0.126735	23.21358	11
M	144.5	-2.44743	17.81463	0.131389	24.22985	12
M	156.5	-2.32946	18.4718	0.134141	25.17811	13
M	168.5	-2.22736	19.15759	0.135251	26.04662	14
M	180.5	-2.13234	19.85766	0.13511	26.83688	15
M	192.5	-2.03902	20.55765	0.134198	27.56393	16
M	204.5	-1.94913	21.24248	0.133057	28.25676	17
M	216.5	-1.87467	21.89587	0.132286	28.95862	18
M	228.5	-1.83514	22.50072	0.132566	29.72674	19
M	240	-1.84233	23.02029	0.134539	30.58964	20
Sex	Age (months)	L	M	S	P95	Age at Screen
F	24	-0.98661	16.4234	0.085452	19.10624	2

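### SAP V.E lets early-termination samples, some drawn weeks after the last dose, stand in as scheduled troughs in the descriptive PK summary

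*SAP*

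**What the plan says.** **Visit mapping.** SAP V.E (Missing Data, Analysis Window) states: "All measurements recorded at unscheduled or early termination visits will be mapped according to the windowed visits by actual study day". It continues: "These records then will be used for analysis if the scheduled ones are missing". No data type is excepted.

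**PK summary.** SAP XI states: "The trough concentration values will be reported descriptively as mean, standard deviation (SD), maximum (Max), minimum (Min), median", together with the percent coefficient of variation, grouped by dose and visit. It gives no on-treatment condition, no limit on time since the last dose, no rule for values below the quantification limit, and no meaning of dose for a patient who has stopped.

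**Draws at Early Termination.** Protocol Tables 1 and 2 both mark trough PK in the Early Termination column. Protocol 5.2 places this visit as follows: "Early Termination visit within 14 days (± 7 days) after the last dose of trial medication". Section 6.3 gives the same timing. Table 1 shows ±5 days for the visit, which needs reconciling with the ±7 in the text but does not change the result.

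**What a trough is.** Protocol 8.6 describes it as a concentration measured before the dose given in the clinic. The drug-supply footnotes (Table 1 footnote 22, Table 2 footnote 20) provide only for return of drug at Early Termination, so no dose is foreseen after that draw.

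**Patients off drug.** Protocol 6.3 adds: "Patients can be offered the option to discontinue trial medication but remain in the trial".

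**Dosing records.** For the draw itself, "For the PK sample, the actual collection (clock) time will be recorded" (Table 1 footnote 18). For home dosing, "A daily question querying whether the patient completed their daily injection will be asked via electronic diary" (footnote 21). Sections 7.5 and 7.6 add a daily dosing log, drug accountability and a trial diary.

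**The concern.** The mapping rule suits weight and BMI, where the SAP's estimand follows a treatment-policy strategy and an off-drug measurement still counts. A trough concentration is a different quantity: exposure about 24 hours after a dose at a given dose level. Under the general rule, a washed-out sample can be labelled with a scheduled visit and pooled with true troughs.

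The mean would then be pulled down and the %CV inflated. The minimum could be driven to about zero by a single patient. A reader of the table could not tell low exposure on drug from absence of drug.

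There is a second route, which does not depend on V.E. A patient who stops drug but stays in the trial may contribute a drug-free sample at a scheduled visit, if PK is drawn there. SAP XI has no condition that would keep such a sample out either.

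**Working it through.** The plan states no figure on this point, so there is none to reproduce.

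**Inputs from the documents**
- Half-life about 10–12 h (Protocol 3.1); once-daily dosing (Protocol 7.3).
- Latest Early Termination draw: 14 + 7 = 21 days after the last dose (Protocol 5.2), or 14 + 5 = 19 days with the Table 1 window.
- Week 16 window for patients not entering Stage 2: Days 99–117 (SAP V.E).
- In-person visits with PK: V5, V7, V10, V12 and V14.

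**1. Is the sample drug-free?** Half-lives elapsed = 24 × days ÷ half-life. Assuming single-exponential decline, the share of the 24 h trough remaining on day d is 2^(−(24d − 24)/t½).

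| Days after last dose | Half-lives elapsed | Share of 24 h trough |
|---|---|---|
| 2 | 4–4.8 | 19–25% |
| 3 | 6–7.2 | 3.6–6.3% |
| 7 | 14–16.8 | 0.005–0.024% |
| 14 | 28–33.6 | 1.5 × 10⁻⁸ or less |
| 21 | 42–50.4 | 10⁻¹² or less |

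From day 7 on, the sample is effectively zero.

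**2. Does the rule place it in a trough row?** Example: last dose Day 88, Early Termination on Day 88 + 14 = 102. Day 102 lies in 99–117 and the scheduled Week 16 sample is missing, so the drug-free value becomes the Week 16 entry.

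**3. How often?** I ran last-dose days spread evenly over each stage (an assumption) through the SAP windows, with draws 7–21 days later and no scheduled visit attended after the last dose.
- About 34% (Stage 1) and 41% (Stage 2) of these samples fill an otherwise missing in-person PK visit.
- About 57% and 50% fall in virtual-visit windows, where no PK is scheduled.
- The rest are displaced by an existing scheduled sample (2–3%) or lie outside every window (6–7%).
- Under other delay assumptions (day 14, day 21, 1–14 days, 1–21 days), 28–44% fill a scheduled PK row.

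**4. What share of a cell?** The documents give no dropout rate. Under the same assumptions, if 20% of patients drop out in each stage and all attend Early Termination, the drug-free share is 3.6% at V5, 4.1% at V7, 3.2% at V10, 3.4% at V12 and 2.6% at V14. A 10% share would need roughly 39–59% dropout in that stage, depending on the visit.

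**5. Effect on the summary.** With a fraction p of values at about zero, the mean becomes (1 − p) times the on-drug mean, and CV becomes √((1 + cv²)/(1 − p) − 1). With an assumed on-drug CV of 50%:
- p = 5%: mean down 5%, CV √(1.25/0.95 − 1) = 56%.
- p = 10%, such as one sample in a cell of 10: mean down 10%, CV √(1.25/0.90 − 1) = 62%.

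Small cells are plausible if the general display rule in SAP V.N, which breaks tables down by gene cohort, is applied to PK: Protocol 5.1.4 aims for up to 10 patients per gene. Reduced-dose groups could also be small.

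**The case against.** The strongest reply is that the text already limits the problem:
- SAP XI groups by dose, and a patient off drug has no current dose, so need not enter the 3 mg cell.
- Protocol 8.6 would disqualify an Early Termination sample, since no dose follows it.
- Values below quantification may be set to missing, in which case they drop out.
- A visit held a day after the last dose yields a genuine trough.
- PK is descriptive, appears in no visible endpoint, feeds no test, and all concentrations are listed.

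These points bound the effect and make it conditional, but they do not close the gap. The SAP neither defines dose after stopping, nor carries the 8.6 condition into XI, nor states a rule for values below quantification. The one rule it does state brings the samples in.

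A reader might also infer more than the documents support:
- **That 10–20% of a cell would be drug-free.** Nothing in the documents supports such shares; in large cells step 4 points to a few percent.
- **That contamination builds up over time and mimics falling exposure or an antibody effect.** Each early terminator gives one such sample, to one window. In step 4 the share is lowest at V14. No visible analysis relates PK to antibodies.
- **That off-drug samples cannot be identified afterwards.** The dosing log, diary and accountability records should identify most of them. Only the clock time of the previous injection is not specified.
- **That patients who stay in the trial off drug certainly add samples.** Section 6.3 mentions weight assessments for them and is silent on PK.

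**Conclusion.** The point holds as a fault in the stated rule, of limited size. Followed literally, SAP V.E and XI can place an essentially drug-free sample in a trough summary, contrary to the protocol's own description of a trough. Patients off drug at scheduled visits may add to this by a separate route.

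The consequence is confined to descriptive PK; the primary endpoint is untouched. The mean shifts in proportion to the drug-free share: about 10% for one sample in a cell of 10, and probably a few percent in large cells. The minimum is the most exposed statistic.

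These sizes assume single-exponential decline at the stated half-life, off-drug values counted as about zero, evenly spread dropout, and attendance at Early Termination. No trend over visits follows from the mapping.

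**What to change.** In SAP XI:
1. Exempt PK concentrations from the V.E mapping rule.
2. Restrict the by-dose-and-visit trough summary to pre-dose samples from patients on active setmelanotide whose dosing records show a dose on the previous day. This covers both routes; exempting Early Termination alone would not.
3. List Early Termination, off-treatment and other samples separately, without pooling them.

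While the section is open, it would help to state how values below quantification are handled and which dose labels a sample.

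The cost is a sentence or two in the SAP and slightly fewer samples in the summary; no data are lost, because everything remains listed. Recording the clock time of the last injection would sharpen the selection, but it is optional. It would mean a protocol amendment with ethics approval across about 80 centers plus an eCRF change, and the core fix does not need it.
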